**Reducing the risk of bias in outcome ascertainment:** Clinicians will continue to send cultures to evaluate neonates for possible infection as part of routine clinical management. The primary care providers in the NICU will not participate in the study and will be masked to the parent-neonate pair assignment. Maintaining masking of the clinicians will reduce the chance that practices for obtaining clinical cultures will differ between the two groups.

The **observation period, or survival time**, is the time that a neonate is at-risk of concordant *S. aureus* acquisition. We will calculate survival time as 1) the interval

between randomization and the date of final culture (either at time of final surveillance culture or at time of discharge culture) for neonates who did not acquire concordant *S. aureus* and 2) the interval between randomization and date of first positive culture for neonates that acquire concordant *S. aureus*.

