## **9. Statistical Analysis Plan**

### **A. Sample size and power estimates:**

The primary outcome will be time to concordant *S. aureus*-colonization. Time to concordant *S. aureus* colonization will be expressed using an indicator variable for concordant colonization and time to concordant colonization. The a priori assumed

control group concordant colonization rate is 10% and power calculations are based on the unadjusted Cox proportional hazards model where the primary covariate is the treatment group indicator. In time to event analyses, power is driven by the number of events; i.e. number of concordant colonizations. Given our assumed control group concordant colonization rate of 10%, 38 events are required to detect a 60 percent reduction in the hazard of concordant colonization (Hazard Ratio: HR 0.4) in the intervention group with 80% power and Type I error rate of 5%. The 38 events includes a roughly 2% inflation for pre-planned interim analyses (see Section 9.B). Given that we expect 5% of the parent-neonate pairs will be non-singleton births, we increased the number of required events to 40 to account for the possible clustering of concordant colonization among non-singleton neonates. Some neonates may test positive at baseline for *S. aureus* after randomization and will not be eligible for the analysis of the primary outcome. Similarly, if one neonate from a multiple gestation birth is positive for *S. aureus* at baseline and another neonate is not, then the negative infant will be eligible. Eligible parent-neonate pairs will be assigned to either treatment or control as a unit until 40 events are confirmed. Prior to the start of the study, given our *a priori* assumption of a 10% concordant colonization rate in the control group and a HR of 0.40, we anticipated recruiting 400 parent-neonate pairs to achieve the required 40 concordant colonizations. With 400 parent-neonate pairs, we have roughly 80% power to detect an absolute risk difference of at least 7% for the secondary analysis of the indicator of concordant colonization within 90 days after randomization.

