## B. Interim Analyses

Several interim analyses will be performed. We will perform interim analyses for efficacy based on the number of accumulated primary outcomes. Specifically, we will perform an interim analysis after 20 and 30 neonates have been identified to have the primary outcome of concordant colonization. After accruing 20 neonates with the primary outcome, the standard Cox proportional hazards model with main effect of treatment will be fit to estimate the treatment effect, i.e. the hazard ratio comparing the hazard of concordant colonization comparing the intervention and control groups, and the test statistic for the treatment effect will be computed using the methods described in Section

9.C. The DSMB will review the results of the Cox proportional hazards model to determine if the trial will stop for efficacy. The **minimum** criteria for stopping for efficacy will be if the test statistic for the hazard ratio is less than  $Z_r = -2.74$ . If the trial continues, after accruing 30 neonates with the primary outcome, the Cox proportional hazards model will be fitted. The DSMB will review the results of these statistical analyses to determine if the trial will stop for efficacy. The **minimum** criteria for stopping for efficacy will be if the test statistic for the hazard ratio is less than  $Z_r = -2.36$ . If the trial continues, after accruing the 40 neonates with the primary outcome, the treatment effect will be deemed statistically significant if the test statistic for the primary analysis as described below falls within the rejection region defined by  $Z_r = -2.03$ .

To define the above rejection regions, we applied an approximation to the error spending function of O'Brien and Fleming ( $f(t) = \min\{at^3, \alpha\}$ ) such that we spend the overall Type I error rate of 0.05 as 0.0062, 0.0148 and 0.029 after accruing 20, 30 and 40 patients, respectively. The derived rejection regions at each interim analysis (i.e.  $Z_r$ ) are based on the hazard ratio (equivalent to the log-rank test comparing the survival experience in the treatment groups) using an approximation to the information available at each interim analysis (i.e. number of accumulated events at the interim analysis divided by 4).

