### **C. Statistical analysis plan**

Final analysis methods and changes in the analyses from those described in the protocol will be documented in the Statistical Analysis Plan prior to locking the database and unmasking the assignment. A CONSORT flow diagram will be created. In addition, descriptive statistics will be calculated to describe the feasibility of the study including number of parent-neonate units approached by a study team member, proportion of parents that consent, proportion of parents colonized among consented, proportion of parents colonized who subsequently do not complete the treatment, and the distribution of adherence, as defined below, to the randomized treatment.

Analyses will be conducted according to the modified intention to treat (mITT) principal. The same day parents are randomized, the neonate will undergo baseline testing to determine baseline *S. aureus* colonization status. Neonates who test positive for *S. aureus* colonization at the time of randomization do not satisfy the inclusion criteria and will not be included in the analysis; hence defining the modified intention to treat analysis. Exploratory analyses of baseline characteristics for the treatment groups will be evaluated by Student t test for continuous data and Pearson's  $\chi^2$  test or Fisher Exact test for categorical data. No missing data should occur for baseline parent and neonate variables. No missing primary or secondary outcomes are expected. However, it is possible that neonates have no subsequent cultures between the baseline culture and NICU discharge, e.g. a neonate enters the study on Friday and is discharged on Sunday prior to their scheduled surveillance culture (Friday in this example) or discharge culture. Based on our definition of observation time (see Sections 5.A and 5.B), such neonates

will contribute no observation time for the analysis of the primary and secondary outcomes. A sensitivity analyses will be conducted where the observation time for these neonates will be defined as the time from randomization to NICU discharge. All tests will be 2-sided with a type-1 error rate set at 0.05. Data will be managed and analyzed using Stata, version 13.0 (Stata Corp., College Station, TX) and R: A language and environment for statistical computing (R Foundation for Statistical Computing, Vienna, Austria, 2014).

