The primary analysis will evaluate our hypothesis that detection and treatment of *S. aureus* colonized parents with intranasal mupirocin and topical chlorhexidine gluconate bathing (Treatment Group) will decrease the risk of a child acquiring *S. aureus* with a concordant strain in the NICU within 90 days of randomization relative to the control parents (Control Group). The parent-neonate pair will be the unit of measure. For neonates that do not acquire concordant colonization within 90 days of randomization, their survival time will be computed as the time from randomization to the date of final culture (surveillance or discharge) within 90 days of randomization. We will define the treatment effect as the relative hazard of concordant colonization comparing the Treatment to Control group and will estimate this hazard ratio using the standard Cox proportional hazards model that includes only a main term for treatment. To account for the possibility of clustering within multiple gestation parent/neonate dyads, standard error estimates and bias-corrected and accelerated (BCa) confidence intervals for the log-hazard ratio will be derived using a bootstrap procedure. To preserve the correlation structure within the dyads, the bootstrap procedure will generate 10,000 bootstrap samples by sampling with replacement the parent/neonate dyads, as opposed to resampling the neonates. The analysis described above will be conducted at each pre-planned interim analysis with the test statistic derived from the estimated log hazard ratio from the Cox model and corresponding bootstrap standard error estimate, and the confidence level for the BCa bootstrap confidence intervals will be determined by the rejection region definitions specified in the Interim Analyses section (see Section 9.B).

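### The event triggers count concordant acquisitions at any time in the NICU, but the primary test counts only those within 90 days, so the looks at 20, 30 and 40 events can hold fewer analysed events than the power calculation assumes

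*Combined protocol and SAP*

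**What the plan says.** **Outcome definition (Section 5.A).** Acquisition is a negative baseline followed by any later surveillance or clinical culture positive for *S. aureus*. Survival time for an event is "the interval between randomization and date of first positive culture for neonates that acquire concordant" *S. aureus*; for other neonates it runs to the final surveillance or discharge culture. No time limit is set.

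**Sample size (Section 9.A).** The assumed "control group concordant colonization rate is 10% and power calculations are based on the unadjusted Cox proportional hazards model"; no time horizon is attached to the 10%. "38 events are required to detect a 60 percent reduction in the hazard of concordant colonization" (hazard ratio 0.40), and this is raised to 40 for multiple births. Pairs are assigned "as a unit until 40 events are confirmed". The 90-day horizon appears in this section only for a binary indicator, which is called a secondary analysis.

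**Interim looks (Section 9.B).** "we will perform an interim analysis after 20 and 30 neonates have been identified to have the primary outcome of concordant colonization". The boundaries are -2.74, -2.36 and -2.03, with information taken as accumulated events divided by 4.

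**Primary analysis (Section 9.C).** The hypothesis concerns acquisition "within 90 days of randomization relative to the control parents". Neonates without an event in that window are censored at their last culture inside it. The same section says that this analysis is run at each planned interim look. The version without the 90-day cut is listed as secondary analysis a).

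**The concern.** In an event-driven trial, the count that triggers a look should be the count that enters the test. Here it need not be. A neonate whose first concordant culture falls after day 90 meets the Section 5.A definition and so counts towards 20, 30 or 40, yet is a censored observation in the Cox model of 9.C.

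Late events are possible under the schedule. Neonates are swabbed weekly until NICU discharge, the parent schedule in Table 1 extends to week 28 and beyond, and infants under 1500 g form a randomization stratum.

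Two things are at stake. The stated 80% power is computed for events that the primary test may not contain. And whoever runs the triggers must decide, without guidance from the plan, whether a late event brings forward a DSMB efficacy look or ends recruitment.

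**Working it through.** **1. Reproduce the plan's event number.** Inputs from 9.A and 9.C: hazard ratio 0.40, 80% power, two-sided 0.05. Equal allocation is taken from Section 4.C.6. Schoenfeld's formula gives

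4 × (1.960 + 0.842)² / (ln 0.40)² = 37.4 events.

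This rounds up to 38, and 37.4 × 1.02 = 38.1 with the 2% allowance for interim looks. For multiples, 38 × 1.05 = 39.9, or 40. The plan's figures reproduce.

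**2. Reproduce the boundaries.** The spending function 0.05 × t³ at t = 0.50, 0.75 and 1 gives increments of 0.00625, 0.0148 and 0.0289, which match 9.B. The probability of crossing -2.74, -2.36 or -2.03 under no effect, with information 20/4, 30/4 and 40/4, is 0.0249 one-sided, or 0.0498 doubled.

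**3. Power when some trigger events fall after day 90.** At each look, Z has mean ln(0.40) × √(events analysed / 4), and the correlation between two looks is √(smaller events / larger events). Power is the probability of crossing any of the three stated boundaries, by multivariate normal integration. The late share is an assumption, taken as equal at each look. The last column divides information by a further 1.05, which is the plan's own allowance for clustering.

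| Late events of 40 | Analysed at final look | Power | Power with 5% clustering allowance |
|---|---|---|---|
| 0 | 40 | 0.816 | 0.797 |
| 2 (5%) | 38 | 0.796 | 0.776 |
| 4 (10%) | 36 | 0.774 | 0.753 |

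**4. Type I error.** If the same share is lost at each look, the ratios between looks do not change and two-sided error stays at 0.0498. In unequal patterns it moves little: analysed counts of 20/27/32 give 0.047, and 14/26/38 give 0.052. What does shift is the amount spent at a given look. With 16 analysed events at the first look, -2.74 spends 0.0061, where 0.05 × (16/40)³ = 0.0032.

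**5. How large might the late share be?** The documents do not say. Section 4.C.1 gives beds and yearly admissions. At full occupancy, mean stay is at most 45 × 365 / 700 = 23.5 days at one site and 25 × 365 / 375 = 24.3 days at the other. These are means over all admissions. Randomized neonates are selected for an anticipated stay longer than 5 days, and those under 1500 g may stay longer, so the mean bounds the share only loosely.

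**The case against.** The best defence is that the plan can be read consistently. Section 9.B triggers on the primary outcome and refers to 9.C for the test statistic, and 9.C runs the 90-day analysis at each look. A reader could therefore take the primary outcome in the trigger to be the 90-day one. That reading is reasonable, but no section states it. Section 5.A, where the outcome is defined, has no limit, and 9.A calls its 90-day indicator secondary. The ambiguity remains.

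Three stronger readings are tempting, and the documents do not support them.

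- *The boundaries fail and type I error is inflated.* A reader might infer this because the boundaries are tied to 20, 30 and 40 events. Step 4 shows overall error between 0.047 and 0.052 in the patterns tried, and 9.B itself calls its information measure an approximation.
- *The power loss is large.* If 8 of 40 events were late, 32 would be analysed and power would be 0.70 to 0.72. Nothing in the documents supports a 20% late share, and a mean stay of at most about 24 days points to a smaller one.
- *The trial has two different primary endpoints.* The event type and the concordance rule are the same throughout; only the horizon differs. Analysis a) in 9.C prespecifies the version without the cut, so late events will still be analysed and reported.

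**Conclusion.** The mismatch is in the text. Section 5.A and the triggers in 9.A and 9.B have no time limit, while the primary test in 9.C has one of 90 days at every look. Followed literally, the looks can contain fewer analysed events than planned.

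The effect is a modest loss of power. Two late events out of 40 give about 0.78 to 0.80 and four give about 0.75 to 0.77, against a stated 80%. These figures assume a hazard ratio of 0.40, proportional hazards, equal allocation and an equal late share at each look; each range runs from with to without the 5% clustering allowance. The late share is unknown and probably small, so the loss may be less. Overall type I error is essentially unchanged at about 0.05, although the information analysed at a look can differ from the stated 20/4, 30/4 and 40/4.

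The point is worth acting on because the design starts at or barely above its target and the correction costs little.

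**What to change.** Use one event definition for the triggers and the primary test. Section 9.C already makes the 90-day analysis primary, so the smallest change is to carry that limit back:

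- In 5.A, add the 90-day limit to the primary outcome and its survival time.
- In 9.A and 9.B, state that only concordant colonizations with a first positive culture within 90 days of randomization count towards 20, 30 and 40.
- Keep the analysis without the 90-day cut as secondary, as now.

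This keeps the sponsor's own analysis, boundaries and 40-event target. The cost is wording in three sections and possibly slightly longer recruitment to reach 40 analysed events. If recruitment is not extended, restate the power for the number of events actually analysed.

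Making the uncensored analysis primary would also remove the mismatch, but it would change the primary analysis that 9.C specifies.

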## 6. Allocation

**Randomization and masking:** This study has taken into consideration the guidelines for reporting of clinical trials as recommended by the CONSORT report to inform the study design. After recruitment and informed consent, parents will undergo pre-randomization screening. If both parents screen negative for *S. aureus* colonization, the neonate will be ineligible for the randomization and parents will be informed that they are not colonized at that time with *S. aureus*. If either parent screens positive for *S. aureus*, then both parents as a pair will be eligible for randomization to one of the two possible masked treatment arms. The neonate-parent "pair" will be the unit of randomization and each parent will be allocated to the same group if both consent. Because couples can re-expose each other after treatment (especially in households) we have chosen to treat both parents even if only one parent is colonized with *S. aureus*. To prevent potential feelings of guilt or one parent blaming another if only one parent is colonized, the parents will be told that one or both is colonized with *S. aureus* and they are eligible for randomization. Discordant parents will not be informed which is colonized and which is not colonized as we will treat both regardless.

Arm 1 will include assignment to masked intranasal mupirocin plus chlorhexidine gluconate cloths for topical antisepsis. Arm 2 will include assignment to masked placebo ointment and placebo cloths for skin antisepsis. Stratified permuted-block randomization will be performed using R statistical software to achieve balanced allocation of subjects within study site (Johns Hopkins Hospital vs. Bayview) and within strata of birth weight

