(greater than or equal to or less than 1500g). Use of varying block sizes (4, 6 and 8) will decrease the risk of imbalance. Neonates of multiple gestations and their parents will be randomized as a single family unit. Investigators and participants will be masked to treatment assignment. The treating clinicians of the neonates will be masked to treatment assignment. The investigational drug pharmacy will use the randomization sequences to prepare supply kits. As subjects are enrolled, they will receive the next kit in sequence based on the study site and birth weight of the neonate. Each kit will contain either active drug or placebo. Active chlorhexidine-impregnated cloths, active mupirocin ointment and their respective placebos will be identified only by lot numbers, and the respective lot numbers will only be known to the investigational drug pharmacist.

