Adverse events, as defined in Section 8, will be reported overall and separately by treatment group. Comparisons across treatment groups will be made using Fisher's Exact tests.

In addition, a series of planned secondary analyses will be conducted including subgroup analyses for the primary outcome, baseline-covariate adjusted analyses for the primary and secondary outcomes, per-protocol (PP) analyses for the primary and secondary outcomes and evaluation of patterns of loss and reacquisition of *S. aureus* among the parents (both treated and control).

Planned subgroup analyses include repeating the analysis for the primary outcome within strata defined by i) neonates with MRSA vs. those with MSSA, ii) collection site of colonization for the parent/caregivers, categorized as nares alone (i.e. all cultured parent/caregivers colonized in the nares) vs. nares + other (i.e. at least one parent/caregiver colonized in the nares) vs. non-nares; iii) LGA (large for gestational age) vs. SGA (small for gestational age); and iv) birthweight (< 1500g vs.  $\geq 1500$ g). The subgroup analyses will be based on Cox proportional hazards models that include a main term for treatment, a main term for subgroup (binary indicator) and the interaction between treatment and subgroup. Confidence intervals and the hypothesis test for no interaction will be derived based on the bootstrap procedure defined above.

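### Randomisation is stratified by hospital and by birth weight at 1500 g, but the primary and interim Cox models use neither factor: a cheap possible gain in precision is passed up (minor)

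*Combined protocol and SAP*

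**What the plan says.** Section 4.C.6 (Allocation) uses stratified permuted blocks of 4, 6 and 8 to obtain "balanced allocation of subjects within study site (Johns Hopkins Hospital vs. Bayview) and within strata of birth weight", the weight strata being "greater than or equal to or less than 1500g". Multiples are randomised with their parents as one family.

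Section 9.A states that "power calculations are based on the unadjusted Cox proportional hazards model where the primary covariate is the treatment group indicator". For the looks at 20 and 30 events, Section 9.B says that "the standard Cox proportional hazards model with main effect of treatment will be fit to estimate the treatment effect". Section 9.C defines the primary effect through a "standard Cox proportional hazards model that includes only a main term for treatment", with standard errors from a bootstrap that resamples families.

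The two factors then fare differently:

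- **Birth weight** is a subgroup factor at 1500 g. There, "The subgroup analyses will be based on Cox proportional hazards models that include a main term for treatment, a main term for subgroup" and an interaction. It is also a continuous covariate in the adjusted secondary analyses.
- **Hospital** is in no named analysis. The collection-site subgroup is anatomical. The inborn/outborn covariate puts both study hospitals in the inborn category, so it cannot separate them. The adjusted analyses announce three covariates and name two. The weighted compliance analysis uses baseline variables that are not listed.

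**The concern.** Factors worth stratifying on are usually those expected to predict outcome. If they do, a model that ignores them pulls the estimated hazard ratio slightly towards 1. It also uses a standard error that misses the precision won by blocking. The planned bootstrap does not recover this, because it is not described as resampling within randomisation strata.

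A hospital difference is plausible here but not shown. Section 4.C.1 describes a 45-bed quaternary unit and a 25-bed level III unit. Section 6.D describes the programme to find and decolonise colonised neonates for Johns Hopkins Hospital, and does not say whether Bayview's is the same. At stake are a few points of power at most, and the lack of any named result that accounts for hospital.

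**Working it through.** **1. The plan's own figure.** Inputs from Section 9.A: hazard ratio (HR) 0.40, 80% power, two-sided 5%, equal arms. Events = 4 × (1.960 + 0.842)² / (ln 0.40)² = 37.4, so 38. With 2% for the interim looks, 37.4 × 1.02 = 38.1. The stated 38 reproduces, and the plan raises it to 40 for multiples. At 40 events, √(40/4) × 0.916 = 2.898. Power is Φ(2.898 − 1.96) = 82.6%, or Φ(2.898 − 2.03) = 80.7% at the final bound. None of this uses the strata.

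**2. Effect of stratifying.** The documents give no hazards by stratum, so each factor was assumed to multiply the hazard by the same amount, in the same direction. Factor HRs of 1, 2, 3, 4 and 5 imply a 1-, 4-, 9-, 16- and 25-fold spread across the four strata. True treatment HR is 0.40. Entries are the change in power in percentage points, stratified minus treatment-only:

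| Simulation | HR 1 | HR 2 | HR 3 | HR 4 | HR 5 |
|---|---|---|---|---|---|
| A. Three looks, family-bootstrap SE | −0.6 | −0.2 | +1.8 | – | +3.5 |
| A. Same trials, model-based SE | −0.9 | −0.2 | +1.7 | – | +2.1 |
| B. Log-rank, singletons | −1.0 | −0.3 | +2.0 | – | +6.2 |
| C. 40 events, Wald, Z < −2.03 | +0.1 | +0.4 | +2.8 | +4.9 | – |
| C. Same trials, absolute Z > 1.96 | 0.0 | +2.0 | +4.7 | +5.9 | – |
| D. 40 events, log-rank, singletons, Z < −2.03 | −0.1 | +1.0 | +2.5 | – | +6.8 |

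A is closest to the plan: 5,000 trials per setting, looks at 20, 30 and 40 events with bounds −2.74, −2.36 and −2.03, blocks of 4/6/8, a 10% control risk, 5% multiples, weekly cultures and a 90-day cap. Its bootstrap power is 72.0 vs 71.4%, 71.7 vs 71.5%, 70.4 vs 72.2% and 68.5 vs 72.0% (treatment-only vs stratified; paired SE of the difference 0.3 to 0.4). C used 4,000 trials per setting and D 3,000. Simulated power lies below the formula values even with no stratum effect, so read the differences and not the levels.

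Site shares follow the admissions in Section 4.C.1: 700/(700 + 375) = 65%. Assumed: 35% of neonates below 1500 g in A and 30% in C; in A also lengths of stay, four families entering per week, and multiples correlated only through shared stratum and arm. A used 200 resamples and SEs only, where the plan has 10,000 and BCa intervals.

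**3. Where the gain comes from.** In C the mean model-based SE is the same for both models (0.353 at factor HR 3). The estimate moves instead: median HR 0.415 treatment-only against 0.405 stratified. In A the medians at 40 events are 0.409 vs 0.405 at factor HR 3 and 0.415 vs 0.402 at factor HR 5.

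**4. Type I error, two-sided.** Treatment-only vs stratified in A with the bootstrap: 2.9 vs 2.9%, 3.1 vs 3.1%, 3.1 vs 3.3% and 2.7 vs 3.2% at factor HR 1, 2, 3 and 5. Monte Carlo SE is √(0.03 × 0.97/5000) = 0.24 points. With model-based SEs, 3.8 vs 3.7%, 3.8 vs 3.9%, 3.7 vs 4.0% and 3.3 vs 3.8%. All are below 5%.

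The treatment-only test is thus conservative even when the strata do not matter. Coarse event counts are one likely reason. Treating the 40 events as a fair binomial split, 14 vs 26 gives Z = ln(26/14)/√(1/14 + 1/26) = 1.87 and 13 vs 27 gives 2.17. Only 13 or fewer in one arm rejects, and that has two-sided probability 3.8%.

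**5. Sparse strata.** A merged the two hospitals within a weight group when either had fewer than 2 pooled events. At HR 0.40 the rule applied in 32, 78, 92 and 99% of trials at 20 events, and in 3, 35, 67 and 92% at 40 events (factor HR 1, 2, 3, 5). Against four full strata it cost at most 0.3 points of power.

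**The case against.** The strongest reply is that the plan's choice is coherent and probably deliberate. Power and stopping bounds rest on the unadjusted model, and covariate adjustment is exploratory, aimed at later trials. The adjusted survival method targets a quantity like the treatment-only HR, whereas a stratified Cox model gives an HR conditional on stratum. This stands: it is why the point is minor, and why the treatment-only HR should be reported alongside.

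A second reply is that the clear gains need a 9- to 25-fold hazard spread with both factors acting together, which is a favourable assumption. That also stands. The simulations do not agree on a flat zero at a factor HR of 2, though: they run from −0.3 to +2.0.

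A third is that merging often removes hospital in at least one weight group, most often where the gain is largest. True, but the gains in simulation A already include that loss.

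A fourth is that hospital may not be absent. The unnamed third covariate could be hospital, and the weighted analysis lists no variables. The supportable statement is only that no named analysis accounts for it.

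**Conclusion.** The point holds as a minor improvement. The primary and interim models ignore both stratification factors, and no named analysis separates the hospitals. Stratifying changes power by about −1 to 0 points with non-prognostic strata, 0 to +2 at factor HR 2, +2 to +5 at HR 3, and +2 to +7 at HR 4 to 5. These ranges rest on the assumed stratum hazards, weight shares and lengths of stay.

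Four stronger readings might be inferred, and none is supported:

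- **That the analysis is invalid or inflates type I error.** In the simulations its error stays below 5%.
- **That hospital confounds the comparison.** Blocking within hospital and weight strata protects balance.
- **That ignoring the strata is what makes the test conservative.** The bootstrap test sits near 3% whether or not they are prognostic.
- **That differing conclusions show a benefit.** In simulation A the two bootstrap tests disagree on efficacy in 3.4 to 6.5% of trials, but 3.4% arises with no stratum effect at all.

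**What to change.** Section 9.C provides that "Final analysis methods and changes in the analyses from those described in the protocol will be documented in the Statistical Analysis Plan" before database lock and unmasking. Make the change there, by staff masked to treatment and to interim results. Which route applies depends on timing, and Section 9.A reads as written after the start: "we anticipated recruiting 400 parent-neonate pairs to achieve the required 40 concordant colonizations".

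**If no interim look has been done:**

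- Stratify the Cox model and its test at every look by hospital and birth-weight group, with treatment as the only term.
- Keep the family bootstrap.
- Fix a merging rule on pooled event counts. For example, merge the two hospitals within a weight group if either has fewer than 2 events, and hold the resulting strata fixed across all resamples of that look.
- Give all neonates of a multiple-birth family the stratum used at randomisation, since siblings may fall either side of 1500 g.
- Label the HR as conditional on stratum and report the treatment-only HR beside it.

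**If a look has already used the treatment-only test:** keep that test as primary and pre-specify the hospital- and weight-stratified Cox model as a sensitivity analysis.

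The first route costs up to about 1 power point if the strata are not prognostic, and changes what the HR means. The second costs no power and gains none for the primary test. Neither needs more events or data: both factors are already held for allocation, and the target stays at 40. As a side note, name the third covariate of the adjusted analyses at the same time.
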